Title: Impacts of inspection during instrument insertion on colonoscopy quality: A prospective randomized controlled trial

INTRODUCTION

Colonoscopy is considered the preferred modality for colorectal cancer (CRC) screening since it has both diagnostic and therapeutic capabilities. However, colonoscopy is not a perfect test. It misses a substantial number of neoplastic lesions [1,2]. In a systematic review of tandem (same-day back-to-back) colonoscopy, the pooled miss rate for polyps of any size was 22%, and the adenoma miss rate by size was 2.1% for ≥ 10 mm, 13% for 6-9 mm, and 26% for ≤ 5 mm, respectively [3]. Researches continue to explore methods to improve the polyp and adenoma detection during colonoscopy and many of them focus on the withdrawal phase of the examination [4-5]. Thus, colonoscopy is typically performed with rapid passage of the instrument through the loops and bends of the colon to the cecum and then performing a slow deliberate withdrawal. As a consequence, all removal of polyps is done when the instrument is pulled back.

Many experienced endoscopists recognized that small polyps seen incidentally but not removed during insertion are sometimes quite difficult to find during withdrawal. This may be due to different anatomical conformations of the colon during instrument insertion and withdrawal. The insertion and withdrawal phases may expose somewhat different sections of the mucosal surface to the colonoscope, and inspection on insertion and withdrawal are possibly complementary. Most endoscopists agree that advanced (≥ 10 mm) polyps should be removed only during withdrawal [6]. Whether smaller polyps (< 10 mm) should be removed during insertion phase is controversial. Some studies showed that inspection and polypectomy during insertion phase reduced colorectal polyp/adenoma miss rate [7-9]. But other studies found that inspection and polypectomy during insertion phase offered no additional benefit on adenoma detection [10-12].

The adenoma detection rate (ADR) has become a validated quality indicator for colonoscopy; the higher the ADR of colonoscopists, the lower the risk of interval CRC and the lower the risk of dying from CRC [13-14]. However, the ADR may not provide a comprehensive assessment of the adequacy and thoroughness of colonoscopic

examination. Recent study has shown that the standard ADR cannot distinguish high versus low endoscopist performance [15]. Other secondary quality measures have been suggested to supplement the ADR and include the polypectomy rate (PR), the mean adenoma per procedure (MAP), the mean adenoma per positive procedure (MAP+), the mean additional adenomas detected beyond the first adenoma per positive procedure (ADR-Plus), and the proximal serrated polyp detection rate (PSP-DR) [15-21]. The impact of the inspection and polypectomy during insertion phase of colonoscopy upon these secondary quality indicators is not known.

The primary aim of this study is to compare the impact upon the colonoscopy quality (including ADR, PR, MAP, MAP+, ADR-Plus, and PSP-DR) of additional inspection and polypectomy during insertion as opposed to the traditional practice of careful inspection and polypectomy performed entirely during withdrawal in patients undergoing routine colonoscopy with moderate sedation for screening or surveillance indications. The secondary aim of this study is to compare the impact of such endoscopic strategy on procedure times, distraction during withdrawal, procedure difficulty, sedative doses, and intra-procedure abdominal pain.

METHODS

This is an investigator-initiated prospective randomized controlled study. The study will be conducted at Evergreen General Hospital, Taoyuan, Taiwan. We plan to enroll patients since October of 2017 and the study is expected to be completed within 18 months after patient enrollment. A written informed consent will be obtained from all patients.

Participants

Patients aged 45 years or older who are able to give informed consent and are scheduled for elective colonoscopy at Evergreen General Hospital are eligible for enrollment. Exclusion criteria are previous surgical resection of the colon or rectum, inflammatory bowel disease, polyposis syndrome, previously incomplete colonoscopy, obstructive lesions of the colon, inadequate bowel preparation (defined as Boston Bowel Preparation Scale [BBPS] score of 0 or 1 in any colon segment) [22,23], gastrointestinal bleeding, allergy to fentanyl or midazolam, American Society of Anesthesiology (ASA) classification of physical status grade 3 or higher, mental

retardation, pregnancy, and refusal to provide a written informed consent. Patients will be enrolled by the primary investigator or co-primary investigators.

Intervention and randomization

Patients will be randomly assigned by a research assistant, by using a computer-generated randomization sequence to undergo colonoscopy with either inspection and polypectomy during both insertion and withdrawal of colonoscope (study group) or inspection and polypectomy entirely during withdrawal of colonoscope (control group). Randomization will be done via concealed allocation with a sealed envelope that designate study group or control group. The colonoscopist is not blinded to group assessment.

Procedure

Colonoscopies will be performed by two experienced colonoscopists by using a standard colonoscopy (CF-Q260AI or CF-Q260AL; Olympus Medical Systems Corp., Tokyo, Japan). All procedures are performed under moderate conscious sedation with fentanyl (United Biomedical, Taipei, Taiwan) and midazolam (Dormicum; Roche Pharmaceuticals, Basel, Switzerland) according to the current guidelines [24]. Carbon dioxide insufflation is used for all endoscopic procedures. All patients receive 3-L polyethylene glycol (PEG; Klean-Prep, Helsinn Birex Pharmaceuticals Ltd., Dublin, Ireland) for bowel preparation. A split-dose of the PEG preparation is provided for morning colonoscopy (2 L consumed in the evening before the colonoscopy and 1 L consumed in the early morning of the colonoscopy) and a same-day preparation is provided for the afternoon colonoscopy. The level of colon cleansing is prospectively evaluated with the BBPS score after all cleansing maneuvers are completed.

For patients in the study group, the colonic lumen is washed with saline and the fluid and debris are suctioned as the instrument is slowly inserted from rectum to cecum. Deliberate and systematic inspection of the colonic mucosa is performed with adequate luminal insufflations during both the insertion and withdrawal phases. Polyp size is determined by comparison with open colonoscopic biopsy forceps pushed against the polyp or, in some cases of pedunculated polyp by direct measurement after retrieval. Polyps with size $<10\text{mm}$ are removed as they are identified on insertion and withdrawal. Polyps with size $\geq10\text{mm}$ are removed only

during withdrawal.

For patients in the control group, deliberate mucosal inspection and polyp removal are performed exclusively on instrument withdrawal. During insertion, minimal mucosal inspection and insufflation are applied to efficiently advance the instrument into cecum. If a polyp is found during insertion, endoscopists are instructed to make a mental note of it and find it during withdrawal for polypectomy.

Definition

Complete colonoscopy is defined as reaching and taking pictures of the cecum and ileocecal valve. Insertion time is defined as the time between the scope insertion and cecal intubation, including the time taken for mucosal clearing and polypectomy. Withdrawal time is defined as the duration between the time at which the cecum is reached and the time at which the scope is withdrawn from the anus, including the time taken for mucosal clearing and polypectomy. Total procedure time is the sum of insertion time and withdrawal time. The quality of bowel preparation is classified as excellent (BBPS score of 8 or higher), good (BBPS score of 7), or fair (BBPS score of 6).

The location of colorectal polyps is defined according to the anatomical distribution. The portion of the colon above the level of the splenic flexure is defined as the proximal colon. Diminutive polyp is defined for polyp with size $\leq 5\text{mm}$. Small polyp is defined for polyp with size 6-9mm. Large polyp is defined for polyp with size $\geq 10\text{mm}$. Adenomas include all adenomas and sessile serrated adenoma. Advanced adenoma is defined as those lesions with one of the following criteria: 1) lesions larger than 10 mm in diameter; 2) lesions with a villous component; 3) lesions with high-grade dysplasia; and 4) lesions with invasive features. ADR is defined as the proportion of colonoscopies where at least one adenoma is found. Advanced ADR is defined as the proportion of colonoscopies where at least one advanced adenoma is found. PR is defined as the proportion of patients undergoing colonoscopy in whom at least one polyp is removed. MAP is defined as the total number of adenomas detected divided by the number of colonoscopies. MAP+ is defined as the total number of adenoma detected divided by the number of colonoscopies in which at least one adenoma is found. ADR-Plus is defined as the mean number of adenomas detected after the first adenoma in procedures in which at least one adenoma is found. PSP-DR is defined as the proportion of patients undergoing colonoscopy in

whom at least one serrated polyp (hyperplastic polyp, sessile serrated adenoma/polyp, traditional serrated adenoma) is identified proximal to the splenic flexure. The mean neoplastic polyp detection rate (MNP-DR) is defined as the total number of adenomas plus proximal serrated polyps (hyperplastic polyp, sessile serrated polyp) divided by the number of colonoscopies.

The grade of the colonoscopy difficulty is rated by the endoscopist using a 10-point Likert scale: 1, being extremely easy; and 10, being extremely difficult. Distraction during withdrawal phase is determined by the time of mucosal clearing and suction divided by the total withdrawal time and the total water volume required for mucosal clearing. Patient's subjective assessment of discomfort during the procedure is graded by patients with a 10-cm visual scale: 0, being no pain; and 10: being extremely severe pain.

Statistical analysis

The primary aim of the study is to evaluate whether there is a difference in the ADR between the two study groups. We calculate the required sample size by using the assumption of a 40% ADR in the control group [25]. For the study to have 85% power to detect a 15% increase in ADR with a 5% significance level, the study needs 211 participants per group to achieve significance (two sided). To account for dropouts, incomplete procedures, and inadequate preparation, an additional 10% will be enrolled. Therefore a total of 464 patients (232 in each group will be enrolled. Summary statistics are presented as frequencies and percentages in the case of categorical variables and as the means with standard deviations in the case of continuous variables. Student's t tests for continuous factors, Wilcoxon rank sum tests for ordinal variables (such as polyp size), and Chi-square tests for categorical variable are uses to assess differences in demographic and clinical characteristics of patients in each group. All calculations are conducted using SAS version 9.3 or later (SAS Institute Inc., Cary, NC, USA). The criterion for statistical significance is $P < 0.05$.

REFERENCES

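### The Introduction puts six detection measures under the primary aim and the Statistical analysis section puts ADR alone there; the Introduction should name ADR as the single primary endpoint

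*Combined protocol and SAP*

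**What the plan says.** The combined protocol and SAP states its primary aim twice.

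- Introduction, aims paragraph: "The primary aim of this study is to compare the impact upon the colonoscopy quality (including ADR, PR, MAP, MAP+, ADR-Plus, and PSP-DR". The next sentence begins "The secondary aim of this study is to compare the impact of such endoscopic strategy on procedure times" and goes on to distraction, difficulty, sedation and pain. PR, MAP, MAP+, ADR-Plus and PSP-DR are not in it.
- Statistical analysis: "The primary aim of the study is to evaluate whether there is a difference in the ADR between the two study groups". The sizing that follows concerns ADR only: "For the study to have 85% power to detect a 15% increase in ADR with a 5% significance level", with 211 per group, two-sided.

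The Introduction's background text leans towards the second statement. It presents the same five measures with the words "Other secondary quality measures have been suggested to supplement the ADR".

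The Statistical analysis section ends with one significance criterion, P below 0.05, and gives no testing order, co-primary rule or multiplicity adjustment.

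**The concern.** The two sentences use the same term for different things, and nothing says which one prevails. The five measures other than ADR appear under no aim except the Introduction's primary one, so a reader cannot dismiss that list as loose phrasing with the proper assignment made elsewhere.

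The consequence lies in what may be claimed at the end. Suppose ADR is not significant and MAP+ has P = 0.04. Under the Statistical analysis section the primary aim has failed. Under the Introduction the authors could report that it was met and cite the protocol in support. The Introduction also argues that ADR on its own is an incomplete measure of quality, which would make that switch easier to defend. The colonoscopist is not blinded, which is a further reason to fix the primary endpoint unambiguously.

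**Working it through.** **Inputs.** From the Statistical analysis section: control ADR 40%; a 15% increase, read as absolute (40% to 55%); two-sided 5%; 85% power; 211 per group; 10% added, giving 232 per group and 464 in total. A relative increase (40% to 46%) would need more than 1,200 per group, so only the absolute reading fits.

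**1. The plan's own figure.** With p1 = 0.40, p2 = 0.55, mean 0.475 and d = 0.15:

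- Uncorrected: n = [1.960 × √(2 × 0.475 × 0.525) + 1.036 × √(0.24 + 0.2475)]² / 0.15² = (1.960 × 0.7062 + 1.036 × 0.6982)² / 0.0225 = 197.5.
- With continuity correction: (n/4) × [1 + √(1 + 4/(n × d))]² = 210.6, so **211 per group**, as stated.
- 211 × 1.10 = 232.1, stated as 232.

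ADR alone, at the full 5%, produces the sample size. Nothing was reserved for other primary tests.

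**2. Number of distinct measures.** By the Definition section, MAP+ is adenomas divided by adenoma-positive procedures. ADR-Plus counts adenomas after the first in the same procedures, so ADR-Plus = MAP+ − 1. The difference between groups and its P value are identical. The six listed measures give five distinct tests.

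**3. If any one measure sufficed (not a rule in the plan).** For five independent tests, 1 − 0.95⁵ = 22.6%. The measures are correlated, so I simulated null trials with 211 per arm and ADR 40% in both arms. The following are assumptions, not figures from the document:

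- PSP-DR 5%, 15%, 25% or 35%.
- Share of PSP-positive patients whose lesion is sessile serrated 0, 50% or 100%. Such a lesion also counts towards ADR, because "Adenomas include all adenomas and sessile serrated adenoma".
- Latent correlation between conventional adenoma and PSP 0, 0.3 or 0.6.
- Mean conventional adenomas per patient with any 1.6, 2 or 3 (geometric).
- Probability of another polyp 2%, 20% or 40%.
- Chi-square tests for ADR, PR and PSP-DR, and t or Wilcoxon tests for MAP and MAP+. The tests had to be assumed because the plan assigns its tests only to "assess differences in demographic and clinical characteristics of patients in each group".

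Results over 648 scenarios of 10,000 trials each:

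| Event in a null trial | Frequency |
|---|---|
| Any measure P < 0.05 | 12.0% to 20.0% |
| ADR not significant, another measure significant | 6.9% to 14.7% |
| Any significant result favouring the study arm | 6.1% to 10.4% |
| All measures significant | at most 0.09% |

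Seven scenarios, including the lowest and highest, were rerun with 40,000 trials each. They gave 12.8% to 19.3% for any measure and 5.1% to 5.3% for ADR alone.

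**4. If all six had to succeed (also not in the plan).** There is no inflation, but power cannot exceed ADR's 85%, and it is at most about 5% if even one measure is unaffected. The plan gives no effects for the other five, so actual power cannot be stated. As illustrations with ADR 40% versus 55%, it is near 0% if PSP-DR and MAP+ do not change. It is about 30% if PSP-DR goes from 15% to 25% and MAP+ from 2 to 2.5.

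**5. Cost of keeping five primaries with Bonferroni (0.05/5 = 0.01 each).** With the continuity correction, ADR power at 211 per group is Φ[(0.15 − 1/211 − 2.576 × 0.04862)/0.04807] = Φ(0.417) = 66%. For 85% power, n = 300.5, so 301 per group. Without the correction the figures are about 70% and 288.

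**The case against.** The strongest reply is that a broad aim in an introduction, with one endpoint used for sizing, is common. The Statistical analysis section is where the endpoint is made operational, and it is unambiguous. The Introduction's background text itself calls the other five secondary. On this view the trial's error rate is 5% and only wording is at fault.

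Much of this stands. ADR is the natural reading, and no planned primary test, sample size or alpha is wrong. But both sentences use the term primary aim, the stated secondary aim omits the five measures, and no text gives one section precedence. A reader must infer the primary endpoint, and authors with a null ADR would have a sentence to cite for inferring otherwise.

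The inflation figures are also open to challenge. They depend on a success rule that the plan does not contain and on assumed rates, and an average over the scenarios would have no evidential meaning, so only the range is used here. The simulated ADR error of 5.1% to 5.3% corresponds to an uncorrected chi-square test, whereas the plan's 211 needs the continuity correction. For that reason the Bonferroni cost is shown both ways. None of these points affects the contradiction, which holds without any simulation.

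**Conclusion.** The concern holds, as something that should be fixed rather than a flaw in the design. The document gives two different primary aims, and its own sample size matches only ADR alone.

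If the Statistical analysis section governs, the primary type I error is 5%. The 12% to 20% range applies only if any one measure at P < 0.05 were treated as success, and it rests on the assumptions listed above. The case of most practical interest, a null ADR with another measure significant, arises in about 7% to 15% of null trials under the same assumptions. Confidence in the contradiction itself is high, because it can be read directly from the text.

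**What to change.** Reword the aims paragraph of the Introduction to agree with the Statistical analysis section: ADR is the single primary endpoint, tested at two-sided 0.05. Move PR, MAP, MAP+, ADR-Plus and PSP-DR to the secondary aim.

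Add a sentence to the Statistical analysis section saying that only the ADR test decides whether the primary aim is met. It should say that the secondary measures are reported as estimates with 95% confidence intervals and that any P values for them are nominal. Note there that MAP+ and ADR-Plus are one comparison, and that both are computed only in adenoma-positive procedures, a subset defined by an outcome after randomisation. Advanced ADR and MNP-DR are defined but belong to no aim, and can be placed in the same edit.

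The cost is a small text change. The 211 per group (464 enrolled), the 5% level and the 85% power for ADR are unchanged. The one thing given up is the option of claiming the primary aim on a measure other than ADR. Keeping five primaries with Bonferroni would cost much more, as step 5 of the working shows.

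### Inadequate preparation is an exclusion that can only act after allocation, and with no analysis set named the primary ADR comparison may not be between the groups as randomised

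*Combined protocol and SAP*

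**What the plan says.** All references are to the combined protocol and SAP.

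- **Participants** lists among the exclusions "inadequate bowel preparation (defined as Boston Bowel Preparation Scale [BBPS] score of 0 or 1 in any colon segment".
- **Procedure** fixes the time of scoring: "The level of colon cleansing is prospectively evaluated with the BBPS score after all cleansing maneuvers are completed". It does not name the scorer.
- **Intervention and randomization** allocates the technique used on insertion and withdrawal, and adds: "The colonoscopist is not blinded to group assessment".
- **Procedure**, for the study group only: "the colonic lumen is washed with saline and the fluid and debris are suctioned as the instrument is slowly inserted from rectum to cecum". Controls have minimal inspection on the way in. They too may be cleared on withdrawal, since Definition says of both groups: "Distraction during withdrawal phase is determined by the time of mucosal clearing and suction divided by the total withdrawal time".
- **Definition** has preparation "classified as excellent (BBPS score of 8 or higher), good (BBPS score of 7), or fair (BBPS score of 6", with no class below 6. It also gives the endpoint: "ADR is defined as the proportion of colonoscopies where at least one adenoma is found".
- **Statistical analysis** plans 211 per group for 40% versus 55% ADR, then: "To account for dropouts, incomplete procedures, and inadequate preparation, an additional 10% will be enrolled". That gives 232 per group. No analysis population is named, and there is no rule for a poorly prepared or incomplete examination.

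**The concern.** An exclusion that depends on something measured after allocation does not have the protection of randomisation. The time of randomisation is not stated, but the arm dictates what happens during insertion, so it must be known before the BBPS can be scored. The score follows cleansing that may differ by arm, and the operator knows the arm. If poorly prepared patients are dropped, and are dropped more often in one arm or have a different ADR by arm, the primary difference is between selected groups.

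The plan points towards dropping them (the exclusion itself, the classes that stop at 6, the inflated enrolment) but never says so, and the ADR definition counts colonoscopies with no condition on preparation. Two analysts could follow this text and report different primary results. Removal of incomplete procedures is a weaker inference, resting only on the pooled allowance.

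**Working it through.** **1. The plan's own figure.** Inputs from Statistical analysis: 40% versus 55%, two-sided 5%, power 85%.

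- Uncorrected: n' = [1.96·√(2·0.475·0.525) + 1.036·√(0.24 + 0.2475)]² / 0.15² = 197.5, so 198.
- With continuity correction: n = (n'/4)·[1 + √(1 + 4/(0.15·n'))]² = 210.6, so 211. This is the stated figure.
- 211 × 1.10 = 232.1, stated as 232. Losing 10% of 232 leaves about 209, with corrected power 84.7%. The trial is therefore sized for a set left after losses.
- Standard error of the difference at 211 per arm: √(0.24/211 + 0.2475/211) = 4.8 points.

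**2. Shift when there is no true effect.** Assume ADR is 40% in both arms among all patients. Let q be the fraction excluded and a the ADR in those excluded; both are assumptions. ADR in the remainder is (0.40 - q·a)/(1 - q).

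Example, 10% control and 5% study excluded, a = 15%: control (0.40 - 0.015)/0.90 = 42.78%; study (0.40 - 0.0075)/0.95 = 41.32%; difference -1.46 points.

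Type I error is by full binomial enumeration of the chi-square test with 232·(1 - q) per arm, rounded.

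| Excluded, control / study | a | Shift, study minus control (points) | Type I error, uncorrected / corrected |
|---|---|---|---|
| 8% / 4%, preparation | 15% | -1.13 | 5.61% / 4.54% |
| 8% / 4%, preparation | 30% | -0.45 | 4.98% / 3.99% |
| 10% / 5%, preparation | 15% | -1.46 | 6.01% / 4.83% |
| 10% / 5%, preparation | 30% | -0.58 | 5.15% / 4.09% |
| 1% / 4%, incomplete | 10% | +0.95 | 5.59% / 4.49% |
| 1% / 4%, incomplete | 20% | +0.63 | 5.30% / 4.25% |
| 13% / 5%, preparation | 10% | -2.90 | 9.19% / 7.57% |
| 13% / 5%, preparation | 30% | -0.97 | 5.46% / 4.34% |

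Equal exclusion rates with equal ADR in the excluded give no shift. With no exclusion bias, the uncorrected test at 211 per arm already has a type I error of 5.2%.

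**3. If washing rescues preparation.** Suppose the rescued study patients rise to the ADR of the others, g = (0.40 - q_c·a)/(1 - q_c), where q_c and q_s are the control and study exclusion fractions. The evaluable-only difference is then 0, while the all-started difference is (q_c - q_s)·(g - a). For 10% / 5% and a = 15%: 0.05 × (0.4278 - 0.15) = +1.39 points. Over the 8% / 4% and 10% / 5% cases the range is +0.43 to +1.39. The evaluable set omits that part of the strategy's effect.

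**4. Power with every started colonoscopy counted.** Exact power, control 40%; study ADR is 0.40 + 0.15·(1 - f), where f is the share of study patients who cannot benefit.

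| n per arm | Study ADR | Power, uncorrected / corrected |
|---|---|---|
| 232, f = 0 | 55% | 89.6% / 87.9% |
| 232, f = 5% | 54.25% | 86.4% / 84.4% |
| 232, f = 9% | 53.65% | 83.5% / 81.1% |
| 211 evaluable, f = 0 | 55% | 86.6% / 84.3% |

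Restoring 85% at f = 9% takes about 240 per arm (249 corrected). If 2% or 5% of each arm have no colonoscopy and count as no adenoma, power is 88.6% or 87.1% (86.8% or 85.1% corrected).

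**The case against.** The strongest reply is that the effect is small and that the documented mechanism is conservative. If washing on insertion means fewer study-arm exclusions, the shift goes against the study arm. In the 8% / 4% and 10% / 5% preparation scenarios, a false result favouring the study arm has probability 1.2% to 2.0% uncorrected, below the nominal 2.5%; at 13% / 5% with a = 10% it is 0.5%. Only the incomplete-procedure scenarios favour the study arm (at most 4.1%), and that exclusion is inferred. The 13% / 5% case is also stretched: it averages 9% for preparation alone, while the plan allows 10% for all losses together. With continuity correction, the first six scenarios stay below 5%.

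This stands as a limit on size. The analysis is not stated to use the correction, however, and a shift against the study arm is still a distortion.

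Arm-dependence is also thinly supported. Controls may be cleared before scoring, the definition of insertion time includes mucosal clearing for everyone, and the scorer is not named. This stands too: differential exclusion is a risk, not a shown fact.

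It can also be said that the exclusion, the classes and the allowance together do settle that poorly prepared patients are out. If so, the denominator is clearer, but the primary comparison is then certainly of groups selected after randomisation. Finally, a set of started colonoscopies is itself a post-randomisation subset. It fits an endpoint defined per colonoscopy, and a sensitivity analysis covers patients who have none.

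**Conclusion.** The concern holds and should be fixed. It is certain from the text that the BBPS exclusion can act only after allocation and that no analysis set is named. Material bias is not certain. With assumed exclusion gaps of 3 to 5 points it is about -1.5 to +0.9 points, with type I error 5.0% to 6.0% (4.0% to 4.8% corrected). It becomes appreciable only with a larger gap and a low ADR in those excluded. All exclusion rates and subgroup ADRs are assumptions, so the size and direction cannot be known in advance. The sample size calculation itself is correct. The selection is avoidable, because whether an adenoma was found can be recorded for every colonoscopy that is started.

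**What to change.** Remove post-allocation BBPS from the exclusion criteria, keep only criteria that can be known before allocation, and add to Statistical analysis:

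> The primary analysis compares ADR in all randomised patients in whom colonoscopy is started, by assigned group; incomplete or poorly prepared examinations count by what was found. Randomised patients with no colonoscopy are reported by arm with reasons, and a sensitivity analysis counts them as no adenoma found. A further sensitivity analysis is restricted to complete examinations with every BBPS segment at least 2. BBPS and reasons for non-evaluability are reported by arm.

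The preparation classes in Definition then need a category below 6.

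The cost is wording, a change in the primary set and two sensitivity analyses; no new data and no extra patients are requested. The stated 85% power should be qualified, because dilution could take it slightly below target, and the sponsor can decide whether that calls for more patients.

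### The time component of distraction during withdrawal is divided by a withdrawal time that includes polypectomy, which the intervention shifts in one arm only; the phase of the water component is not stated

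*Combined protocol and SAP*

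**What the plan says.** The last paragraph of the INTRODUCTION gives the secondary aim as a comparison of "procedure times, distraction during withdrawal, procedure difficulty, sedative doses, and intra-procedure abdominal pain". The Definition subsection of METHODS then opens its rule with "Distraction during withdrawal phase is determined by" and names two components: "the time of mucosal clearing and suction divided by the total withdrawal time and the total water volume required for mucosal clearing".

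Three other statements decide how the rule behaves:

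- **Denominator.** Under Definition, withdrawal time runs from reaching the cecum to "the time at which the scope is withdrawn from the anus, including the time taken for mucosal clearing and polypectomy".
- **When polyps are removed.** Under Procedure, study-group polyps under 10 mm "are removed as they are identified on insertion and withdrawal", and larger ones are removed on withdrawal only. For controls, "deliberate mucosal inspection and polyp removal are performed exclusively on instrument withdrawal".
- **Washing on insertion.** The study-group procedure states that "the colonic lumen is washed with saline and the fluid and debris are suctioned as the instrument is slowly inserted from rectum to cecum". The control procedure describes no such step.

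The Statistical analysis subsection does not mention distraction, and no other section adjusts the measure or says which phase the water volume covers.

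**The concern.** The measure should show how far cleaning interrupts inspection on withdrawal. Its denominator, however, contains a quantity that the randomized strategy itself changes. Removing small polyps on insertion takes polypectomy time out of withdrawal in the study group but not in the control group. The ratio can then differ between arms with no difference in clearing.

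The rule also works against its own purpose. Polypectomy on withdrawal is itself an interruption of inspection, yet the more of it there is, the lower the distraction score.

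At stake is the reading of one named secondary aim. Less cleaning on withdrawal is a benefit that insertion washing might plausibly bring, and a modest benefit of that kind could be cancelled or shown as harm. The water component adds a separate uncertainty. The sentence concerns withdrawal, but the volume is described only as a total, and one arm is washed on the way in.

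**Working it through.** The plan states no value for distraction, so there is no figure to reproduce. The check is algebra, followed by illustration with assumed minutes.

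**Notation** (minutes on withdrawal): i = inspection, c = clearing and suction, p = polypectomy in the control group, m = share of p moved to insertion in the study group. The numerator is read as withdrawal time only.

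- Control ratio: c / (i + c + p)
- Study ratio with equal i and c: c / (i + c + p(1 − m))
- Relative artefact: (i + c + p) / (i + c + p(1 − m)) − 1. This is positive whenever m > 0 and p > 0, and zero when polypectomy time on withdrawal is equal in the arms.
- Break-even: the two ratios are equal when study-group clearing c′ satisfies c′/c = (i + p(1 − m)) / (i + p), which is a fall in clearing of mp / (i + p).

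**Worked example** (assumed i = 6, c = 2, p = 4, m = 0.5)

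- Control: 2/12 = 16.7%.
- Study, same clearing: 2/10 = 20.0%, or +20% relative.
- Study, clearing down 15% to 1.7 min: 1.7/9.7 = 17.5%, so a real reduction reads as an increase.
- Break-even fall: 0.5 × 4 / (6 + 4) = 20%. Check: 1.6/9.6 = 16.7%, equal to control.

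**Range** (assumed i = 6-8, c = 1-3, p = 2-6, m = 0.3-0.7)

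- Smallest artefact (i = 8, c = 3, p = 2, m = 0.3): 13/12.4, or +5%.
- Largest artefact (i = 6, c = 1, p = 6, m = 0.7): 13/8.8, or +48%.
- Smallest break-even fall: 0.6/10 = 6%. Largest: 4.2/12 = 35%.

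**A second set of assumptions** with less polypectomy (i = 6-10, c = 1-3, p = 1-4, 25-75% remaining on withdrawal) gives +0.2 to +6.9 percentage points. At i = 8, c = 2, p = 2 with 25% remaining, the ratios are 2/12 = 16.7% and 2/10.5 = 19.0%. A fall in clearing to 1.7 min gives 1.7/10.2 = 16.7%, so a 15% reduction would be exactly hidden.

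**With polypectomy removed from the denominator**, the ratio is c / (i + c), which is the same in both arms when i and c are the same. At i = 8 and c = 2 it is 2/10 = 20.0% in each.

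**Water.** If the volume covers withdrawal only, moving polypectomy or washing on insertion adds nothing to it. If it covers the whole procedure, study-group insertion water enters a measure labelled as withdrawal. The text does not settle which.

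**The case against.** **The net direction is unknown.** The ratio is misleading in a known direction only when clearing is equal or nearly so, and the design makes equal clearing unlikely, because the study group is washed and suctioned on insertion. In the worked example a fall of more than 20% gives the right direction, and a fall above 35% does so everywhere in the first range. This stands. A reader might infer that the trial will report more distraction in the study group; the documents do not support that, because they give no clearing times. What they support is a distortion under equal clearing, and a threshold below which a true reduction is lost.

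**Water.** A reader might also infer that the measure counts water from both phases, so that both components lean against the study group. The text does not say so. The opening words of the sentence can govern both components, and a total may mean the total used on withdrawal. This stands too: the finding on water is ambiguity, with bias under one reading only.

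**Size.** Every minute is assumed. Polypectomy time must be averaged over all patients, including those with no polyp, who contribute no artefact, and the 48% figure combines extreme values. Polyps of 10 mm or more, and small ones first seen on withdrawal, stay in the denominator. These points limit the size but do not alter the algebra.

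**Planned data.** Procedure times are also a secondary aim, and clearing must be timed to form the ratio, so a careful reader could see a shorter study-group withdrawal. The share of withdrawal spent cleaning is also a coherent description. But the plan does not commit to reporting clearing minutes alone, and it is the ratio that carries the label of distraction.

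**Conclusion.** The point holds for the time component. As defined, it is higher in the study group whenever clearing and inspection are equal and less polypectomy time remains on withdrawal. This follows from the definitions and the two procedures and needs no assumed minutes.

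The size cannot be derived from the documents. Under the first set of assumptions it is +5% to +48% relative. A true fall in clearing smaller than the break-even (6-35%, and 20% in the worked example) would be reversed, one equal to it would be hidden, and a larger one would show in the right direction. The water component is unclear rather than shown to be biased.

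The definition should be corrected, but the issue is confined to one secondary measure. The ADR comparison and its sample size do not depend on it.

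**What to change.** - **Time component.** Define it as absolute minutes of mucosal clearing and suction during withdrawal, compared between arms. This is already timed for the numerator and needs no new data.
- **Ratio.** Make any ratio secondary. If it is kept, use withdrawal time net of polypectomy as the denominator.
- **Water component.** Specify the volume instilled during withdrawal only, and report total water over both phases separately as a measure of burden.

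The cost is a change of wording and one water-volume reading at cecal intubation. Polypectomy time on withdrawal has to be noted only if the net ratio is kept. Both items must be recorded during the procedure and probably cannot be recovered later, so the change belongs before enrolment. If data have already been collected without them, absolute clearing minutes can still be reported beside the ratio and withdrawal time by arm.
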